### **5.3 Removal of Subjects from Study Participation**

Subjects will be informed that they are free to withdraw from the study at any time and for any reason. The Investigator (or designee) may remove a subject from the study if, in the Investigator's (or designee's) opinion, it is not in the best interest of the subject to continue the study. Subjects may be withdrawn due to the following: change in compliance with inclusion/exclusion criterion that is clinically relevant and affects subject safety, occurrence of AEs, intake of nonpermitted concomitant medication that might affect subject safety or study assessments/objectives, etc. Notification of withdrawal will immediately be made to the Sponsor's Study Monitor. In case of withdrawal of study participation, efforts will be made to perform all final study day assessments ([Table 6-1](#)). The date the subject is withdrawn from the study and the reason for withdrawal will be recorded on the subject's Case Report Form (CRF). All withdrawn subjects will be followed until resolution of all their AEs or until the unresolved AEs are judged by the Investigator (or designee) to have stabilized.

The entire study may be discontinued at the discretion of the Investigator (or designee), Sponsor, or Sponsor's Medical Monitor based on the occurrence of the following:

- AEs unknown to date with respect to their nature, severity, and/or duration;
- increased frequency and/or severity and/or duration of known AEs;
- medical or ethical reasons affecting the continued performance of the study;
- difficulties in the recruitment of subjects;

- cancellation of drug development.

## **6 STUDY PROCEDURES**

### **6.1 Schedule of Study Procedures**

A study flow chart is presented in [Table 6-1](#). The total blood volume that will be taken during the study is outlined in [Appendix B](#).

**Table 6-1 Study Flow Chart**

	Screening	Check -in									Discharge	Follow-up Phone Call
Study Procedures	Days (-29 through -2)	Day -1	Day 1	Day 2	Day 3	Day 4	Day 5	Day 6	Day 7	Day 8	(Day 9 or up to Day 14) a	4 ± 2 days after Discharge
Informed Consent	X											
Demographics	X											
Medical History	X	X b										
Height, Weight, and BMI	X	X c										
Hepatitis and HIV Screen	X											
Alcohol and Drug Screen d	X	X										
Pregnancy Test e	X	X										
FSH f	X											
Confined to the Clinical Site		X	X	X	X	X	X	X	X	X	X	
Physical Examination		X									X g	
C-SSRS h	X	X		X							X	
Vital Signs i	X	X	X	X	X	X	X	X	X	X	X	
Orthostatic Vital Signs j	X	X	X									
12-lead ECG k	X	X									X	

	Screening	Check -in									Discharge	Follow-up Phone Call
Study Procedures	Days (-29 through -2)	Day -1	Day 1	Day 2	Day 3	Day 4	Day 5	Day 6	Day 7	Day 8	(Day 9 or up to Day 14) a	4 ± 2 days after Discharge
Clinical Chemistry Panel, Complete Blood Count, Urinalysis	X	X		X							X	
SAE Monitoring l	X	X	X	X	X	X	X	X	X	X	X	X
AE Monitoring m			X	X	X	X	X	X	X	X	X	X
Prior/Concomitant Medication Monitoring	X	X	X	X	X	X	X	X	X	X	X	X
[  C]-Lasmiditan Administration n			X									
Pharmacokinetic/ Radioactivity Blood Samples o			X	X	X	X	X	X	X	X	X	
Metabolism Blood Samples p			X	X		X	X					
Urine Samples q			X	X	X	X	X	X	X	X	X	
Fecal Samples r			X	X	X	X	X	X	X	X	X	

AE = adverse event; BMI = body mass index; C-SSRS = Columbia Suicide Severity Rating Scale; ECG = electrocardiogram; FSH = follicle-stimulating hormone; HIV = human immunodeficiency virus; SAE = serious adverse event

a Early termination procedures to be performed in close proximity to discontinuation of subject from the study. Other procedures may be performed at Investigator (or designee) or Sponsor discretion.

b Interim medical history only.

c Weight only.

---

d Drug screen does not include alcohol testing at Screening but does include an alcohol breath test at Check-in (Day -1).

e Females only. A serum pregnancy test will be collected at Screening and Check-in.

f To confirm postmenopausal status in females only.

g Abbreviated physical examination only.

h A baseline version of the C-SSRS survey will be given at Screening and the “since last visit” version of the C-SSRS will be given at Check-in, on Day 2, and at Discharge.

i Vital sign measurements (oral temperature, respiratory rate, and seated blood pressure and pulse) will be obtained at single timepoints at Screening, Check-in, and at 1, 2, 4, 24, 48, 72, 96, 120, 168, and 192 hours postdose. If the subject is not discharged on Day 9, additional vital sign measurements will be performed every 24 hours until Discharge. Vital sign measurements will be performed with the subject in a seated position after the subject has rested for at least 5 minutes. When the timepoints for blood draws and vital sign measurements coincide, the vital sign measurements will be collected prior to the blood draws and as close to the scheduled timepoint as possible.

j Orthostatic blood pressure and pulse will be obtained at Screening, Check-in, at 0 Hour (predose), and at 1.25, 1.75, and 2.25 hours postdose. Blood pressure and pulse will first be collected with the subject in a seated position after the subject has rested for at least 5 minutes. Blood pressure and pulse will be taken again after the subject has been standing for 2 to 4 minutes. The same arm will be used during each assessment of blood pressure and pulse. When the timepoints for blood draws and orthostatic vital sign measurements coincide, the orthostatic vital sign measurements will be collected prior to the blood draws and as close to the scheduled timepoint as possible.

k Single 12-lead ECGs obtained at Screening, Check-in, and Discharge. The 12-lead ECGs will be collected after the subject has been resting in a supine position for at least 10 minutes. When the timepoints for blood draws and ECGs coincide, the ECGs will be collected prior to the blood draws and as close to the scheduled timepoint as possible.

l Any SAEs occurring after the subject signs the Informed Consent Form will be recorded.

m Subjects will be monitored for AEs beginning at initiation of study drug. An AE inquiry will be performed at each postdose vital sign measurement.

n Single oral dose of [C]-lasmiditan at 200 mg (approximately 100 µCi) administered orally to subjects in a fasted state.

o Blood samples for pharmacokinetics and radioanalysis will be collected at 0 Hour (predose) and at 1, 2, 3, 4, 5, 6, 8, 12, 24, 36, 48, 72, 96, 120, 144, 168, and 192 hours postdose. If the subject is not discharged on Day 9, additional blood samples will be collected every 24 hours until Discharge. If the plasma radioactivity levels fall below the limit of quantitation, then samples for radioanalysis will no longer be collected.

p Blood samples for metabolite profiling and identification collected at 0 Hour (predose) and at 2, 4, 8, 24, 72, and 96 hours postdose.

q Urine samples collected at -12 to 0 hours (predose, the last void within 1 hour prior to dosing) and at the following collection intervals: 0 to 6, 6 to 12, 12 to 24, 24 to 48, 48 to 72, 72 to 96, 96 to 120, 120 to 144, 144 to 168, and 168 to 192 hours postdose. If the subject is not discharged on Day 9 (after the 192 hour postdose timepoint), then urine will be collected at 24-hour intervals until Discharge.

r If possible, a baseline fecal sample will be collected predose (within 24 hours of dosing). Fecal samples will also be collected daily (24-hour intervals) from Days 1 through 9. If a subject is not discharged on Day 9, then fecal samples will be collected at 24-hour intervals until Discharge.

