**Figure 4-1 Study Design Schematic**

PK = pharmacokinetic.

Note: Single oral dose of [C]-lasmiditan at 200 mg (approximately 100 µCi) administered orally to subjects in a fasted state.

Subjects will be confined at the clinical site from the time of Check-in (Day -1) until Discharge (between Days 9 and 14, inclusive). After completing discharge procedures, subjects will be discharged from the clinical site on Day 14 or as early as Day 9, provided radioactivity has reached all of the following threshold values:

- plasma radioactivity levels below the limit of quantitation; AND
- $\geq 90\%$  of the dose is recovered; AND
- urine total radioactivity  $\leq 1\%$  of the administered dose for 2 consecutive 24-hour intervals; AND
- fecal total radioactivity  $\leq 1\%$  of the administered dose for 2 consecutive 24-hour intervals.

Sample collection and confinement will continue until discharge criteria are met or the maximum stay (Day 14) is reached, unless otherwise agreed upon by the Sponsor and Investigator. A Follow-up Phone Call will be conducted  $4 \pm 2$  days after Discharge.

Subjects experiencing emesis during the first 4 hours postdose may be discharged on the same day from the clinical site, provided there are no safety concerns, and after follow-up study procedures are performed. Subjects who are discharged from the study early will not be replaced.

Safety will be monitored with AE inquiries, clinical laboratory evaluations ([Appendix A](#)), vital sign measurements (including orthostatic vital sign measurements), 12-lead electrocardiograms (ECGs), physical examination findings, and the Columbia Suicide Severity Rating Scale (C-SSRS) during the study.

Pharmacokinetic and radioanalytical samples will be obtained through at least 192 hours (8 days) postdose and metabolism samples will be obtained through 96 hours (4 days) postdose. A study flow chart is presented in [Table 6-1](#).

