10.3 Pharmacokinetic Assessment

10.3.1 Pharmacokinetic Analysis

The following pharmacokinetic parameters will be determined, where possible, based on the plasma concentrations of lasmiditan, metabolites M3, M7, M8, and M18 and total radioactivity in whole blood and plasma, using non-compartmental methods performed using Phoenix WinNonlin (Certara United States, Inc.) version 6.4 or higher:

Parameter	Definition
$AUC_{0-t_{last}}$	Area under the concentration-time curve from time 0 to the time of last measurable concentration (t_{last}), calculated using the linear trapezoidal rule for increasing concentrations and the logarithmic rule for decreasing concentrations
$AUC_{0-\infty}$	Area under the concentration-time curve from time 0 extrapolated to infinity
$\%AUC_{(t_{last}-\infty)}$	Percentage of AUC that is due to extrapolation from the last measurable concentration to infinity
C_{max}	Maximum observed concentration
t_{max}	Time of maximum observed concentration
t_{last}	Time of last quantifiable concentration
$t_{1/2}$	Apparent terminal elimination half-life
λ_z	Apparent terminal elimination rate constant, where λ_z is the magnitude of the slope of the linear regression of the log concentration versus time profile during the terminal phase
CL/F	Apparent oral clearance (calculated for lasmitidan only)
V_z/F	Apparent volume of distribution during the terminal elimination phase (calculated for lasmitidan only)
AUC Ratio (Blood /Plasma)	$AUC_{0-\infty}$ of total radioactivity in whole blood/ $AUC_{0-\infty}$ of total radioactivity in plasma
AUC Ratio (Lasmitidan/TRA)	$AUC_{0-\infty}$ of lasmitidan in plasma/ $AUC_{0-\infty}$ of total radioactivity in plasma

AUC Ratio (Metabolite/TRA) $AUC_{0-\infty}$ of metabolite in plasma/ $AUC_{0-\infty}$ of total radioactivity in plasma (calculated for each metabolite)

M:P AUC Ratio Metabolite to lasmitidan (parent) ratio calculated as:
 $AUC_{0-\infty}$ metabolite/ $AUC_{0-\infty}$ lasmitidan

$AUC_{0-\infty}$, CL/F, and V_z/F will be calculated based on predicted Clast.

In addition, the following PK parameters will be calculated, whenever possible, for each subject based on the urine concentrations of lasmitidan, metabolites M3, M7, M8, M18 and total radioactivity. Parameters for lasmitidan and metabolites will be reported by the Covance Early Clinical Biometrics PK group; parameters for total radioactivity will be reported by the Covance Radioanalysis group.

Parameter	Definition

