The amount excreted in urine (A_{eu}) for each urine collection interval will be calculated as the product of urine concentration and urine weight (assuming specific gravity is approximately 1); Total $A_{eu_{0-xh}}$ will be calculated by summing the A_{eu} values for each collection interval over the study collection period, where x is the end time of the last collection interval.

The percent of the dose excreted (%UR) will be calculated for each urine collection interval (i) according to the following formula:

$$\%UR(i) = \frac{A_{eu}(i)}{\text{dose}} \times 100$$

Total %UR will be calculated by summing the %UR values for each collection interval over the study collection period.

CL_R will be calculated over 0-x h according to the following formula:

$$CL_R = \frac{\text{Total } A_{eu_{0-xh}}}{AUC_{0-xh}}$$

10.3.1.1 Criteria for handling concentrations below the limit of quantification in Pharmacokinetic analysis

- Concentration values that are below the level of quantification (BLQ) will be set to zero, with defined exceptions as follows;
- Any embedded BLQ value (between 2 quantifiable concentrations) and BLQ values following the last quantifiable concentration in a profile will be set to missing for the purposes of PK analysis.
- If there are late positive concentration values following 2 BLQ concentration values in the apparent terminal phase, these values will be evaluated. If these values are considered to be anomalous, they will be set to missing.
- If an entire concentration-time profile is BLQ, the profile will be excluded from the PK analysis.
- If a predose concentration is missing, it may be set to zero with sponsor approval

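### The stop rule for blood radioanalysis does not say whether it can act before 192 hours, and it looks only at plasma although a whole-blood/plasma AUC ratio is planned

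*Protocol*

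**What the plan says.** Footnote o belongs to the blood-sample row for pharmacokinetics and radioactivity in Protocol Table 6-1. It lists 18 times from predose to 192 hours and continues: "If the subject is not discharged on Day 9, additional blood samples will be collected every 24 hours until Discharge". The next sentence is the stop rule: "If the plasma radioactivity levels fall below the limit of quantitation, then samples for radioanalysis will no longer be collected". It states no start time and no condition on whole blood.

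Protocol 4.1 says "Pharmacokinetic and radioanalytical samples will be obtained through at least 192 hours (8 days) postdose", with no exception. The synopsis and SAP Section 6 say the same. Protocol 4.1 also says "Sample collection and confinement will continue until discharge criteria are met or the maximum stay (Day 14) is reached", unless the sponsor and investigator agree otherwise. Plasma radioactivity below the limit of quantitation (BLQ) is one of four discharge criteria, and all four must be met.

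Protocol 6.4.6 has total radioactivity measured separately in whole blood and plasma. Protocol 7.3 and SAP 10.3.1 define AUC0-∞ for each and the ratio of blood to plasma.

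The other matrices have their own footnotes with no BLQ stop. For urine, past Day 9, "then urine will be collected at 24-hour intervals until Discharge"; for feces, "then fecal samples will be collected at 24-hour intervals until Discharge".

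**The concern.** There are two problems.

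The first is timing. Nothing in footnote o confines the stop rule to samples after 192 hours, so a site could apply it to the scheduled samples and fall short of the minimum in Protocol 4.1. Different staff could also apply it differently to different subjects.

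The second is the trigger. A plasma result ends sampling in both matrices. If radioactivity persists in whole blood after plasma is BLQ, the late blood points are never drawn. The terminal slope is then fitted to the faster, earlier part of the curve, and blood AUC0-∞ and the blood/plasma ratio come out too low. Samples not drawn cannot be recovered, and only 8 subjects are planned.

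**Working it through.** **Sample count.** Footnote o has 18 times: 0, 1, 2, 3, 4, 5, 6, 8, 12, 24, 36, 48, 72, 96, 120, 144, 168 and 192 h. Daily samples on Days 10 to 14 fall at 24 × (day − 1) = 216, 240, 264, 288 and 312 h. So 18 + 5 = 23, and 23 × 10 mL = 230 mL, which reproduces Appendix B. The blood budget therefore assumes no early stop.

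**Scheduled samples lost on the literal reading.** If plasma is first BLQ at 48 h, the samples at 72, 96, 120, 144, 168 and 192 h are not drawn: 6 of 18. A first BLQ at 96 h loses 4, and at 144 h loses 2.

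**Effect on the ratio.** The documents give neither assay limits nor blood/plasma partition data, so everything below is assumed.

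- Plasma radioactivity: C(t) ∝ ka/(ka − k) × (e^(−kt) − e^(−ka·t)), ka = 1.2/h, scaled to a maximum of 1, half-life 6, 12 or 18 h. For orientation, Protocol 2.1.2.1 gives mean half-lives of 4.66 to 6.38 h for lasmiditan and above 12 h for reduced metabolites.
- Cmax is 50 or 200 times the limit, with the same limit in both matrices.
- Each plasma result is known before the next draw. A reporting delay would reduce the loss.
- Blood is either (a) 0.7, 1.0 or 1.3 times plasma throughout, or 0.7 times plasma plus a slow term f × (1 − e^(−0.3t)) × 2^(−t/h), with (b) f = 2% of plasma Cmax and h = 60 h, or (c) f = 5% and h = 100 h.
- AUC uses the linear-up/log-down rule. AUC0-∞ = AUC0-tlast + predicted Clast/λz, as in SAP 10.3.1, with λz from the best-fitting terminal points (at least three, after Cmax).

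The change is the stopped ratio over the ratio with sampling to 312 h, minus 1, from unrounded values.

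| Plasma t½ (h) | Cmax/limit | First plasma BLQ (h) | (a) change | (b) change | (c) ratio, full → stopped | (c) change | (c) extrapolated after stop |
|---|---|---|---|---|---|---|---|
| 6 | 50 | 48 | 0% | 0.0% | 1.345 → 0.915 | −31.9% | 4.2% |
| 6 | 200 | 72 | 0% | −7.1% | 1.351 → 0.981 | −27.4% | 2.9% |
| 12 | 50 | 72 | 0% | 0.0% | 0.978 → 0.867 | −11.3% | 4.9% |
| 12 | 200 | 96 | 0% | −0.7% | 1.055 → 0.895 | −15.1% | 3.1% |
| 18 | 50 | 120 | 0% | 0.0% | 0.898 → 0.859 | −4.4% | 3.3% |
| 18 | 200 | 144 | 0% | 0.0% | 0.945 → 0.898 | −5.0% | 5.2% |

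The literal rule acts before 192 h in all six settings. Quantifiable blood samples lost, counting to 312 h, are 0 in (a), 0 to 2 in (b) and 1 to 10 in (c).

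**Would the SAP notice?** SAP 10.3.1.3 flags AUC0-∞ at 20 to 30% extrapolation and excludes it from descriptive statistics above 30%. After truncation in (c) the apparent extrapolation is 2.9 to 5.2%, so nothing is flagged. The partial-AUC fallbacks in SAP 10.3.1 and 10.3.1.3 apply when AUC0-∞ cannot be determined. Here it can be determined but is wrong.

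**If the rule acts only after 192 h.** With blood sampled to 192 h, the ratio in (c) stays close to the full value. The largest gap is 0.929 against 0.945, that is 0.929/0.945 − 1 = −1.7%. In (a) and (b) there is no change to three decimals.

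**The case against.** The strongest reply is that the stop rule directly follows the sentence on samples after Day 9 and is meant only for those. A subject kept in the unit solely by the recovery, urine or fecal criteria would then be spared further blood radioanalysis, and the 192-hour minimum would stand. That reading is plausible, so a reader who infers a certain contradiction goes too far. But the footnote does not say it, whereas footnote q ties its own extension explicitly to the 192-hour point. The plasma-only trigger also survives that reading, though at little cost in the scenarios above.

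The other objections narrow the point:

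- A reader might infer that all radioanalysis stops. It does not. Urine and feces run to discharge, so mass balance is untouched, and the rule does not stop lasmiditan blood samples.
- A reader might infer that the blood curve will be truncated. That happens only if blood stays quantifiable after plasma does not, and nothing in the documents shows this.
- One could assume a single 24-hour blood half-life and note that 2^(−36/24) = 35% or 2^(−48/24) = 25% of the area is left to extrapolate. In that model log-linear extrapolation recovers AUC0-∞, so it shows no bias. Bias needs a slower phase that the truncated curve misses.
- A reader might fear that one chance BLQ result costs later plasma points. From 48 h draws are 24 h apart. A level of 1.2 or 1.1 times the limit is still quantifiable at the next draw only if the half-life exceeds 24 × ln 2/ln 1.2 ≈ 91 h or 24 × ln 2/ln 1.1 ≈ 175 h. The loss is negligible at the half-lives considered.
- The SAP 10.3.1.1 provision that begins "If there are late positive concentration values following 2 BLQ concentration values in the apparent terminal phase" could not operate for radioactivity if sampling ended at the first BLQ. It is a general contingency that still serves lasmiditan and its metabolites, so this is a side effect, not a separate defect.

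The affected output is a descriptive ratio with no formal analysis. That limits the consequence but does not remove it, because the ratio is a planned parameter.

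**Conclusion.** The concern holds in a limited form. Footnote o and the 192-hour minimum must be reconciled: they conflict on the literal reading and agree on the other, and the text does not choose. On both readings the rule stops whole-blood sampling on a result that says nothing about whole blood.

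The size is unknown. On the literal reading and the stated assumptions, the blood/plasma ratio is unchanged if blood parallels plasma. It moves by 0 to −7% with a small slow blood component and by −4 to −32% with a larger one, without a flag from the SAP limits. If the rule acts only after 192 h, the same scenarios give 0 to about −2%. Most of the risk therefore lies in the missing time limit. The range depends wholly on the assumed slow component and assay limits; it is not a forecast for lasmiditan. The edit is worth making because it is cheap and missed samples cannot be replaced.

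**What to change.** Amend footnote o to say three things: blood radioanalysis sampling runs to 192 h for every subject; the stop rule applies only to the 24-hourly samples after 192 h; and it takes effect only when both plasma and whole-blood radioactivity are BLQ. The synopsis, Protocol 4.1 and SAP Section 6 can then keep their 192-hour wording. Protocol 4.1's sentence on continuing collection until discharge should note this one exception. The discharge criteria need not change.

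The cost is one footnote, one cross-reference and some extra scintillation counts returned as BLQ. The planned maximum stays at 18 + 5 = 23 samples and 230 mL.

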## 6.2 Study Treatment

### 6.2.1 Drug Supplies and Accountability

The Sponsor (or designee) will provide the Investigator (or designee) with adequate quantities of the study drugs (Table 6-2).

**Table 6-2 Study Drugs**

Study Drug	[  C]-Lasmiditan	Lasmiditan
Form a	Powder	Powder
Specific Activity	0.5µCi/mg	Not applicable
Supplier	ARCINOVA Ltd.	Aptuit (UK) Ltd. OR Produits Chimiques Auxillaires et de Synthèse (PCAS)
Manufacturer	ARCINOVA Ltd.	Aptuit (UK) Ltd. OR Produits Chimiques Auxillaires et de Synthèse (PCAS)

aSpecific ingredients/purity will be identified in the Certificate of Analysis (or equivalent) that is supplied with the study drug(s).

The lot numbers for the study drug(s) will be provided to the clinical site by the supplier/manufacturer as soon as available.

Nonradiolabeled study drugs will be stored at room temperature (between 15°C and 30°C) under secure conditions and protected from light). Radiolabeled study drug will be stored in a freezer set to maintain -80°C (±10°C).

The Investigator (or designee) will maintain an accurate record of the receipt of the clinical trial materials as shipped by the Sponsor (or designee), including the date received. One copy of this receipt will be returned to the Sponsor when the contents of the shipment have been verified. In addition, an accurate drug disposition record will be kept, specifying the amount dispensed to each subject and the date of dispensation. This drug accountability record will be available for inspection at any time. At the completion of the study, the original drug accountability record will be available for review by the Sponsor on request.

At the completion of the study, all unused drug supplies will be returned to the Sponsor (or designee) or disposed of by the clinical site, per the Sponsor's (or designee's) written instructions.

